3.1 Study Objectives

3.1.1 Primary Objective

To determine whether a starting dose of lenvatinib 18 mg once daily (QD) will provide comparable efficacy (based on objective response rate [ORR] at 24 weeks [ORR_{24wk}]) with an improved safety profile compared to 24 mg QD (based on treatment-emergent adverse events [TEAEs] of Grade 3 or higher in the first 24 weeks after randomization).

3.1.2 Secondary Objectives

- To evaluate progression-free survival (PFS) in subjects treated with lenvatinib doses of 24 mg and 18 mg QD
- To evaluate the PFS after next line of treatment (PFS2) in subjects treated with lenvatinib doses of 24 mg and 18 mg QD.
- To evaluate the safety and tolerability of lenvatinib doses of 24 mg and 18 mg QD.
- To evaluate the PK/pharmacodynamic relationship between exposure and biomarkers/efficacy/safety, using a mechanistically based approach, if possible.
- To evaluate the impact of lenvatinib treatment on HRQoL as measured by the instruments EQ-5D-3L and FACT-G.

3.1.3 Exploratory Objectives

- To explore overall survival (OS) in subjects treated with lenvatinib doses of 24 mg and 18 mg QD.
- To explore thyroglobulin, thyroid-stimulating hormone (TSH), and other serum biomarkers as potential biomarkers for tumor response.
- To explore DNA sequence variants in genes that might influence PK, safety, or pharmacodynamics data.

3.2 Overall Study Design and Plan

This was a multicenter, randomized, double-blind study being conducted as a postmarketing commitment to the US Food and Drug Administration (FDA) and the European Medicines Agency (EMA) to evaluate whether there was a lower starting dosage of lenvatinib other than 24 mg QD that could provide comparable efficacy but have a better safety profile in subjects with RR-DTC with radiographic evidence of disease progression (PD) within the prior 12 months.

Eligible subjects should have measurable disease according to Response Evaluation Criteria in Solid Tumors Version 1.1 (RECIST 1.1) and evidence of PD within 13 months before signing informed consent (both assessed by independent radiologic review) and were randomly assigned to treatment in a 1:1 ratio to receive lenvatinib 24 mg or 18 mg orally QD. The total sample size is 152 subjects (76 subjects per arm). Randomization was stratified by age (≤ 65 years or >65 years) and Eastern Cooperative Oncology Group (ECOG) performance status (PS) of 0 vs 1 or 2. Study ended when the last subject enrolled completed the Week 24 tumor assessments or discontinued study drug before Week 24. Subjects received study treatment until disease progression, development of unacceptable toxicity, subject requested to discontinue, withdrew consent or was lost to follow-up, end of the study, or until study termination by the sponsor. After PD was observed, subjects were followed for PFS2 and survival.

This study consisted of 2 phases: the Prerandomization/Pretreatment Phase and the Randomization/Treatment Phase (see Figure 1). The Schedules of Procedures and Assessments for both study phases are explained in Table 7 of Protocol Amendment 05. Per protocol, tumor assessments were performed during the Prerandomization Phase and then every 8 weeks (within the 8th week) from the date of randomization during treatment cycles in the Randomization Phase. Subjects who discontinued treatment without PD in the Randomization Phase continued to undergo tumor assessments every 8 weeks until PD was documented or another anticancer therapy was initiated. Subjects were then followed every 12 weeks (± 1 week) for survival, PFS2 and all subsequent anticancer treatments received (unless this information was not allowed to be provided due to confidentiality) had been recorded until the End of Study.

[figure not shown]

Figure 1. Study Design for Study E7080-G000-211 (as of Protocol Amendment 05)

PD = progressive disease, PFS2 = progression-free survival after next line of anticancer treatment, QD = once daily.

4 DETERMINATION OF SAMPLE SIZE

Sample size determination was based on the number of subjects required to detect noninferiority of the primary efficacy endpoint, ORR_{24wk} , comparing the 18 mg arm to the 24 mg arm. Based on the data from Study 303, the ORR_{24wk} for the lenvatinib 24 mg arm was 54.4% (142 responders, N=261) and 0.8 % for the placebo arm (1 responder, N=131) and the lower 95% CI of the Odds Ratio for lenvatinib 24 mg vs placebo was 21.4. Assuming a 70% retention of the effect of lenvatinib 24 mg versus placebo, the noninferiority margin on the Odds Ratio scale was estimated to be 0.40 (i.e, H_a : Odds Ratio [18 mg/24 mg] >0.4).

A sample size of 152 subjects (76 per arm) would provide a statistical power of 80% to declare noninferiority, assuming a 1-sided alpha of 0.025, an ORR_{24wk} of 54.4% for lenvatinib 24 mg and a true Odds Ratio of 1, with a noninferiority margin of 0.4.

For the primary safety endpoint, based on data from Study 303, where 70.5% of subjects in the lenvatinib 24 mg arm had a TEAE of Common Terminology Criteria for Adverse Events (CTCAE) Grade 3 or higher during the first 24 weeks, the sample size of 152 subjects provides a precision for the observed differences between the arms with half-widths of the 95% CI of about 15%.

5 STATISTICAL METHODS

All descriptive statistics for continuous variables will be reported using mean, standard deviation, median, 1st quartile (Q1), 3rd quartile (Q3), and minimum and maximum values and will be specified in the outputs. Categorical variables will be summarized as the number (percentage) of subjects.

Unless otherwise specified, summary reporting will be presented by lenvatinib starting dose (24 mg, 18 mg) and overall treatment; the analysis set to be used is explained in [Table 1 \(Section 5.2.1\)](#).

5.1 Study Endpoints

All study planned analysis endpoints are explained in this section. Per protocol, tumor assessment related endpoints will be defined based on investigator review per RECIST 1.1. The tumor assessment schedules are described in Table 7 of Protocol Amendment 05.

5.1.1 Primary Endpoints

- ORR_{24wk} as assessed by the investigator using RECIST 1.1. ORR_{24wk} is defined as the proportion of subjects with best overall response (BOR) of complete response (CR) or partial response (PR) at the Week 24 time point or earlier. The BOR for each subject will be determined based on RECIST 1.1 without a requirement for response confirmation.
- Rate of TEAEs with CTCAE grades of 3 or higher within 24 weeks after randomization (as of the Week 24 time point).

5.1.2 Secondary Endpoints

- PFS, defined as the time from the date of randomization to the date of first documentation of disease progression, or date of death, whichever occurs first
- PFS2, defined as the time from randomization to second objective disease progression (occurring during treatment with next line of anticancer therapy), or death from any cause, whichever occurs first
- Overall safety profile and tolerability
- Time to treatment discontinuation due to an adverse event (AE)
- Number of dose reductions

- Time to first dose reduction
 - *Plasma PK lenvatinib exposure parameters
 - *Interrelationships of lenvatinib exposure, changes in thyroglobulin, TSH, or other exploratory serum biomarkers, and changes in tumor burden and PFS
 - *Relationship of lenvatinib exposure and changes in blood pressure (BP), and AEs of weight loss, fatigue, nausea, vomiting, diarrhea, and proteinuria CTCAE grades derived from urine protein measurements
 - *Impact of lenvatinib treatment on HRQoL as assessed using the validated instruments EQ-5D-3L and FACT-G
- * Will be provided in separate reports.

5.1.3 Exploratory Endpoints

- Duration of response, defined as the time from the initial achievement of a response (CR or PR) to the date of first documentation of disease progression, or the date of death, whichever occurs first
 - Disease control rate (DCR), defined as the proportion of subjects who have BOR of CR, PR, or stable disease (SD). BOR of SD must be achieved at least 7 weeks after randomization
 - Clinical benefit rate (CBR), defined as the proportion of subjects who have BOR of CR, PR, or durable SD (duration of SD \geq 23 weeks after randomization)
 - OS, measured from the date of randomization until date of death from any cause
 - *Associations between objective tumor response and serum thyroglobulin (accounting for anti-Tg), TSH, and other serum biomarkers (including VEGF, Ang-2, sTie-2, and FGF23)
 - *Association between any observed DNA sequence variability and PK, pharmacodynamic, and clinical outcome measures including efficacy and safety-related endpoints
- * Will be provided in a separate report.

5.2 Study Subjects

5.2.1 Definitions of Analysis Sets

Full Analysis Set will include all randomized subjects. This will be the analysis set for all efficacy evaluations, which will be analyzed according to the treatment randomized, regardless of the treatment actually received.

Safety Analysis Set will include all subjects randomized and received at least one dose of study drug. This will be the analysis set for all safety evaluations, which will be analyzed according to the treatment actually received.

Pharmacokinetic (PK) Analysis Set will include all subjects who received at least one dose of study drug and who have evaluable lenvatinib plasma concentration data.

The parameters analyzed for each analysis set are listed in Table 1.

Table 1 Analysis Sets

Analyses to be performed	Analysis Sets			
	Enrolled Subjects	Full Analysis Set	Safety Analysis Set	PK Analysis Set
Protocol Deviations		•		
Disposition	•			
Demography & Baseline Characteristics		•		
Disease History		•		
Prior & Concomitant Medications		•		
Progression-Free Survival		•		
Progression-Free Survival 2		•		
Overall Survival		•		
Tumor Response		•		
Drug Exposure			•	
Adverse Events			•	
Deaths	•		•	
Laboratory Tests			•	
Vital Signs			•	
Electrocardiograms (ECGs)			•	
Echocardiography			•	
Pharmacokinetics				•
Clinical Biomarkers			•	

5.2.2 Subject Disposition

The number of subjects enrolled and the number (percentage) of subjects who were screen failures and the primary reason for screen failure will be summarized based on data from the Case Report Form (CRF) of Screening Disposition.

The number of subjects screened, randomized, treated, and with major protocol deviations will be counted by site. Subject disposition on study treatment (treatment ongoing at data cutoff date, treatment discontinued, and the primary reason for discontinuation) will be

summarized. Study status at data cutoff and reason for withdrawal from the study will also be summarized using data from survival follow-up.

5.2.3 Protocol Deviations

Major protocol deviation criteria will be established and all subjects with potential major protocol deviations will be identified and reviewed in a blinded manner prior to database lock. Major protocol deviations will be summarized by each category and will be listed.

5.2.4 Demographic and Other Baseline Characteristics

Demographic and other baseline characteristics will be summarized. Continuous demographic and baseline variables include age, body weight and height, body mass index (BMI), categorical variables include sex, age group (≤ 65 , >65), race, ethnicity, region, body weight group (<60 kg, ≥ 60 kg), ECOG (0, 1, 2), New York Heart Association (NYHA) classification, and baseline TSH (≤ 0.5 , >0.5 to 2.0, >2.0 to 5.5 $\mu\text{IU/mL}$).

DISEASE HISTORY

Disease history and characteristics at study entry will be summarized based on data recorded on the CRFs, including thyroid cancer pTNM staging at diagnosis, DTC subtype diagnosis, stage group at diagnosis, time since diagnosis (original and metastatic), and prior therapy (anticancer medications, radiotherapy, previous radioiodine therapy). In addition, locally advanced or metastatic DTC will be characterized using the location of both target and nontarget lesions at screening, and summarized. The number of metastatic sites per subject will also be included in the summary table.

MEDICAL HISTORY

Subjects with any previous medical condition and current medical condition, as recorded on the CRF, will be summarized by system organ class (SOC) and preferred term (PT). The Medical Dictionary for Regulatory Activities (MedDRA) version 23.0 will be used.

5.2.5 Prior and Concomitant Therapy

All investigator terms for medications recorded in the CRF will be coded to an 11-digit code using the World Health Organization Drug Dictionary (WHO DD) Version (WHODDMAR20B3). Prior medications will be defined as medications that started before the first dose of study drug. Concomitant medications will be defined as medications that (1) started before the first dose of study drug and were continuing at the time of the first dose of study drug, or (2) started on or after the date of the first dose of study drug up to 28 days after the subject's last dose. Medications that cannot be determined to be prior/concomitant/posttreatment because of missing or incomplete dates will be regarded as concomitant.

The number (percentage) of subjects who took prior medications will be summarized by anatomical class (Anatomical Therapeutic Chemical [ATC] Level 1), pharmacological class (ATC Level 3), and World Health Organization Drug Name (preferred term). The same summary will be repeated for concomitant medications except for thyroxine suppression therapy and antihypertensive therapy. Concomitant thyroxine suppression therapy and antihypertensive therapy will be summarized separately. In addition, there will be a separate summary for P-glycoprotein inhibitors and/or inducers taken as concomitant medications.

5.2.5.1 Previous Therapies

Previous chemotherapy, VEGF-targeted therapy, radiotherapy, radioiodine therapy, and antithyroid cancer surgery will be summarized, and listings will be provided for previous anticancer medications, radioiodine therapy, and radiotherapy.

Prior database lock, previous chemotherapy and previous VEGF-targeted therapy will be identified by the clinical and coding team based on data from the Previous Anticancer Medications CRF page. Similarly, previous antithyroid cancer surgery will be identified from the Medical History CRF page.

5.2.6 Treatment Compliance

Treatment compliance will be summarized by the number (percentage) of subjects with any drug interruption not due to investigator request. In addition, the percentage of days that study drug was interrupted not due to investigator request will be calculated.

5.3 Data Analysis General Considerations

5.3.1 Pooling of Centers

This is a multicenter study. Subjects from all centers will be pooled for all analyses.

5.3.2 Adjustments for Covariates

Not applicable.

5.3.3 Multiple Comparisons/Multiplicity

Not applicable.

5.3.4 Examination of Subgroups

No subgroup analyses are planned for this study.

5.3.5 Handling of Missing Data, Dropouts, and Outliers

Rules for handling full/partial missing dates, and the censoring rules for PFS, PFS2, and OS are explained in [Section 8.4](#). The handling of missing data in the analyses of ORR, CBR and

DCR is explained in Sections 5.4. Any potential outlier values will be investigated and will be analyzed in the locked database as originally reported.

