#### 9.7.1.6 Efficacy Analyses

All efficacy analyses will be performed on the Full Analysis Set. For subjects who were randomized before implementation of Amendment 03, efficacy results will not be included in the analyses, but will be included in a separate report.

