8.5 Missing Date Handling

Missing data will not be imputed unless otherwise stated in the SAP or in the footnote of an output. Missing data will not be included in any analysis unless otherwise specified. When relevant, the number of subjects with missing data will be presented.

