8.5.1 Adverse Event with Missing Dates

If the missing start and/or end dates of the AE do not indicate that the AE started prior to the start of study drug or after the 28th day after the last dose of study drug, it will be classified conservatively as a TEAE ([Section 5.6.2](#)). This data handling is only for the determination of TEAEs; no imputation will be performed to AE start/end dates in datasets and listings.

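### Does the SAP leave subjects without a post-baseline scan unassigned in the primary response analysis?

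*SAP*

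**What the plan says.** SAP 5.3.5 makes two cross-references. The first ("Rules for handling full/partial missing dates, and the censoring rules for PFS, PFS2, and OS are explained in") points the reader to 8.4. The second opens with "The handling of missing data in the analyses of ORR, CBR and" and closes by sending the reader elsewhere: "DCR is explained in Sections 5.4".

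Section 5.4 has three parts. 5.4.1 gives the stratified CMH odds ratio, the 0.4 margin and normal-approximation intervals for the rates and their difference. 5.4.2 gives the PFS and PFS2 methods. 5.4.3 covers duration of response, DCR and CBR (by the ORR24wk method), OS and waterfall plots. None says how a subject without an evaluable post-baseline scan is counted.

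Elsewhere:

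- SAP 5.2.1 defines the Full Analysis Set as all randomized subjects and adds "This will be the analysis set for all efficacy evaluations". Table 1 there places tumor response on that set.
- Protocol 9.7.1.6 agrees: "All efficacy analyses will be performed on the Full Analysis Set".
- SAP 5.1.1 gives this definition for ORR24wk: "proportion of subjects with best overall response (BOR) of complete response (CR) or partial response (PR) at the Week 24 time point or earlier".
- SAP 8.5, titled Missing Date Handling, contains the sentence "Missing data will not be included in any analysis unless otherwise specified". Its two subsections are "8.5.1 Adverse Event with Missing Dates" and a matching one for medication dates, which refers back to 5.2.5.

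**The concern.** A section on missing data that points to a rule which does not exist deserves a second look, especially when the rule concerns the primary endpoint. A programmer who follows 5.3.5 to 5.4 and finds nothing might fall back on 8.5, whose wording covers any analysis, and drop unscanned subjects from the response rate. The denominator would then be evaluable subjects instead of all randomized subjects. That is a different estimand, in the one analysis on which noninferiority is decided. If more unscanned subjects were dropped from one arm than from the other, the odds ratio itself would shift, in either direction.

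Other references in the SAP are also wrong, which makes the text look less carefully checked than it should be:

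- 5.6.1 cites 5.4.1 for the PFS method, which is in 5.4.2.
- 5.6.2 cites Appendix 13.2 for the clinically significant events, which are listed in 13.1.
- 5.6.3 cites a protocol Appendix 13.8 that does not exist.
- 5.4.3 speaks of two endpoints after naming one, apparently a remnant of duration of clinical benefit, which Section 7 drops.

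**Working it through.** **1. The plan's own figure.** Inputs from SAP Section 4: response 54.4% in both arms (true OR 1), margin 0.4, 1-sided alpha 0.025, power 80%. On the log odds ratio scale,

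n per arm = (1.960 + 0.842)² × [2 / (0.544 × 0.456)] / (ln 0.4)² = 75.4, rounded up to 76.

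Power at 76 per arm is 80.3%. The margin also reproduces: 21.4^(−0.3) = 0.399. These figures contain no allowance for non-evaluable subjects, which fits an analysis of all 152 randomized subjects.

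**2. What the text implies.**

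- Denominator: the Full Analysis Set, so 76 + 76 if recruitment meets the plan.
- Numerator: subjects who have a CR or PR by Week 24. A subject with no scan has neither.
- The response variable is therefore yes or no for everyone randomized, and no value is missing for 8.5 to act on. The same holds for DCR and CBR, whose numerators also require an achieved response category.
- The 8.5 sentence yields wherever something else is specified, and 5.2.1 with Table 1 specifies the set for tumor response.

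**3. What the wrong reading would cost.** The documents give no number of unscanned subjects, so the counts below are assumptions. The limit is the unstratified Wald one,

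lower limit = OR × exp(−1.96 × √(1/a + 1/b + 1/c + 1/d)),

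where a and b are responders and nonresponders on 18 mg, and c and d the same on 24 mg. The 24-mg arm has 41 responders, about 54% of 76.

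| 18 mg | 24 mg | Dropped | Lower limit | Above 0.4? |
|---|---|---|---|---|
| 41/76 | 41/76 | none | 0.528 | yes |
| 41/74 | 41/71 | 2 and 5 | 0.471 | yes |
| 36/76 | 41/76 | none | 0.406 | yes |
| 35/76 | 41/76 | none | 0.385 | no |
| 36/75 | 41/75 | 1 per arm | 0.403 | yes |
| 36/74 | 41/74 | 2 per arm | 0.3995 | no |
| 36/76 | 41/75 | 1 on 24 mg | 0.394 | no |
| 37/76 | 41/75 | 1 on 24 mg | 0.415 | yes |

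With everyone counted, the smallest passing 18-mg count is 36. Dropping one subject in each arm leaves it at 36. Dropping one from the 24-mg arm alone moves it to 37.

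**4. How often the two readings would disagree.** With j unscanned on 18 mg and k on 24 mg, responders among the scanned are binomial with 76 − j and 76 − k subjects and probabilities 0.544 × 76/(76 − j) and 0.544 × 76/(76 − k), so the all-randomized rate is 54.4% in both arms. Summing over all pairs in which one reading passes and the other fails:

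| Unscanned (18 mg, 24 mg) | Disagreement |
|---|---|
| 1, 1 | 1.1% |
| 2, 2 | 3.8% |
| 0, 1 | 4.0% |
| 1, 0 | 0.9% |

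In the one-arm rows the rates among scanned subjects differ by construction, so part of the disagreement reflects a different estimand.

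**5. The other pointers.** Section 8.4 does hold the PFS, PFS2 and OS censoring rules, so that reference is right for censoring and wrong only for missing dates, which are in 8.5, with medication dates in 5.2.5. For 5.6.3, CTCAE is in protocol Appendix 6, and the SAP's contents also list its own CTCAE appendix as 13.6. None of these slips changes a computed quantity.

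**The case for a change.** The best argument for acting is that an analysis set says who is in the population, not how a missing outcome within it is classified. 5.3.5 promises that classification, 5.4 does not give it, and the only general sentence left points toward exclusion. Larger or unequal losses would also matter more than the small cases above. With 36 responders on 18 mg against 41 and four unscanned per arm, the limit goes from 0.406 to 0.392. With 35 against 41, and eight unscanned on 18 mg and four on 24 mg, it goes from 0.385 to 0.412. A few sentences before database lock would cost almost nothing.

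The textual point stands: the promised rule is absent. The distinction between population and classification is sound in general but has little force here, because the endpoint counts an achieved response, and not achieving one is already a classification. The fallback to 8.5 requires the programmer to overlook the section's title, its date-only subsections, its exception clause and Table 1 together. The losses of four to eight subjects are assumptions without support in the documents. The dataset specifications and table shells, which the SAP keeps in separate documents, may state the rule outright, but they cannot be inspected here.

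**Conclusion.** The concern identifies a real drafting slip, but not a defect in the analysis. The plan already fixes an all-randomized denominator for ORR24wk, and by the same method for overall ORR, DCR and CBR, with unscanned subjects counted as not responding. Under that reading the effect on the estimate, the test, the sample size and the power is zero. An added sentence would restate what the analysis set, Table 1 and the endpoint definition give together, and the remaining reference errors are clerical.

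The near-margin figures, about 1% to 4% disagreement, apply only if 8.5 is misread. They rest on assumed counts of one or two unscanned subjects, a 54.4% response rate in both arms and an unstratified Wald interval, whereas the planned test is a stratified CMH odds ratio. The exact responder counts therefore do not carry over to the actual analysis. No change to the plan follows.
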